10.5 ADDITIONAL INFORMATION REGARDING IN/EX CRITERIA

Reversibility testing (P05-12782)

At the screening visit (Visit 1), following the completion of three acceptable pre-bronchodilator forced expiratory manoeuvres, albuterol will be administered to each patient in order to document the degree of reversibility. Immediately after (within 10 min) pre-bronchodilator forced expiratory manoeuvres and after a gentle and incomplete expiration, a dose of 100 µg of salbutamol (albuterol) is inhaled in one breath to total lung capacity (TLC). The breath is then held for 5–10 s before the subject exhales. Four separate doses (total dose 400 µg) are delivered at approximately 30-s intervals (this dose ensures that the response is high on the salbutamol dose–response curve). Three additional, acceptable post-bronchodilator forced expiratory manoeuvre tests are recorded ≥10 minutes and up to 45 minutes later after the last dose of albuterol is inhaled.

Calculation of predicted normal values according to ECSC (R94-1408)

For height measured in inches

Males: FEV_1 predicted (L) = 4.30 x [height (inches)/39.37] - 0.029 x [age (yrs)] - 2.49

Females: FEV_1 predicted (L) = 3.95 x [height (inches)/39.37] - 0.025 x [age (yrs)] - 2.60

For height measured in meters

Males: FEV_1 predicted (L) = 4.30 x [height (m)] - 0.029 x [age (yrs)] - 2.49

Females: FEV_1 predicted (L) = 3.95 x [height (m)] - 0.025 x [age (yrs)] - 2.60

Calculation of number of pack years

$$\text{Pack years} = \frac{\text{Number of cigarettes/day}}{20} \times \text{years of smoking}$$

Boehringer Ingelheim

BI Trial No.: 1237-0063

c13020187-03

06 March 2018

Trial Protocol

Page 94 of 125

Proprietary confidential information © 2018 Boehringer Ingelheim International GmbH or one or more of its affiliated companies

Boehringer Ingelheim

BI Trial No.: 1237-0063

c13020187-03

06 March 2018

Trial Protocol

Page 95 of 125

Proprietary confidential information © 2018 Boehringer Ingelheim International GmbH or one or more of its affiliated companies

Boehringer Ingelheim

BI Trial No.: 1237-0063

c13020187-03

06 March 2018

Trial Protocol

Page 96 of 125

Proprietary confidential information © 2018 Boehringer Ingelheim International GmbH or one or more of its affiliated companies

Boehringer Ingelheim

BI Trial No.: 1237-0063

c13020187-03

06 March 2018

Trial Protocol

Page 97 of 125

11. DESCRIPTION OF GLOBAL AMENDMENT(S)

11.1 GLOBAL AMENDMENT 1

| | | |
|--|---|--|
| Number of global amendment | | 1.0 |
| Date of CTP revision | | 11 August 2017 |
| EudraCT number | | N/A |
| BI Trial number | | 1237-0063 |
| BI Investigational Product(s) | | Stiolto® Tiotropium+olodaterol |
| Title of protocol | | A randomized, double-blind, double-dummy, active-controlled, multi-center, parallel group study to show the superiority in lung function of 12 weeks once daily treatment with orally inhaled tiotropium+olodaterol fixed dose combination delivered by the Respimat® inhaler vs. 12 weeks twice daily treatment with orally inhaled fluticasone propionate+salmeterol fixed dose combination delivered by the Diskus® in patients with Chronic Obstructive Pulmonary Disease (COPD) [ENERGITO® 2] |
| To be implemented only after approval of the IRB / IEC / Competent Authorities | X | |
| To be implemented immediately in order to eliminate hazard – IRB / IEC / Competent Authority to be notified of change with request for approval | | |
| Can be implemented without IRB / IEC / Competent Authority approval as changes involve logistical or administrative aspects only | | |
| Section to be changed | | Section 3.3 |
| Description of change | | Exclusion criterion updated to soften contraception requirements. |
| Rationale for change | | To be consistent with current guidance on trials with approved drugs, and to reduce discrepancies in messaging for contraception / fertility / etc. between the IC / protocol and the publically |

| | | |
|------------------------------|--|---|
| | | available drug label. |
| | | |
| Section to be changed | | Section 3.3.4.1 |
| Description of change | | Removal of the sentence: Details of all COPD exacerbations will be captured in the source notes and on AE/SAE pages. |
| Rationale for change | | As it is not an exacerbation trial, details of exacerbation events will not be collected in this trial. |
| | | |
| Section to be changed | | Section 5.1.3 and Section 7.3 |
| Description of change | | FVC added to further endpoints FAS updated |
| Rationale for change | | To analyse collected endpoints and to keep consistency with 1237.11. To be able to have in the full analysis dataset and therefore to analyze the patients for efficacy if they have missing PFTs but they have other efficacy endpoints collected like SGRQ or CAT. |
| | | |
| Section to be changed | | |
| Description of change | | Revised sentences to add “or designee” and removed the following sentence: If a trial collaborator has given a supplementary explanation, the trial collaborator also signs (or places a seal on) and dates the informed consent. |
| Rationale for change | | In the US, per FDA regulations, the PI can delegate responsibilities, including consenting of subjects to study team. |
| | | |
| Section to be changed | | Appendix 10.1 |
| Description of change | | Replace Respimat® instructions for use |
| Rationale for change | | Respimat® instructions have been updated |

11.2 GLOBAL AMENDMENT 2

| | | |
|--|---|--|
| Date of amendment | | 06 March 2018 |
| EudraCT number | | NA |
| EU number | | |
| BI Trial number | | 1237-0063 |
| BI Investigational Product(s) | | Stiolto® Tiotropium+olodaterol |
| Title of protocol | | A randomized, double-blind, double-dummy, active-controlled, multi-center, parallel group study to show the superiority in lung function of 12 weeks once daily treatment with orally inhaled tiotropium+olodaterol fixed dose combination delivered by the Respimat® inhaler vs. 12 weeks twice daily treatment with orally inhaled fluticasone propionate+salmeterol fixed dose combination delivered by the Diskus® in patients with Chronic Obstructive Pulmonary Disease (COPD) [ENERGITO® 2] |
| To be implemented only after approval of the IRB / IEC / Competent Authorities | X | |
| To be implemented immediately in order to eliminate hazard – IRB / IEC / Competent Authority to be notified of change with request for approval | | |
| Can be implemented without IRB / IEC / Competent Authority approval as changes involve logistical or administrative aspects only | | |
| Section to be changed | | |

| | | |
|------------------------------|--|---|
| | | randomized at one site. |
| | | |
| Section to be changed | | Flow Chart and Guidance notes – pages 5-6 |
| Description of change | | 1. Register patient in screening (IRT) changed from visit 1 to visit 0; 2. #16: remove “once daily”3. Footnote 6 – added “if needed” |
| Rationale for change | | 1. Patient numbers must be received when the patient consents, which is at visit 0; 2. Error in guidance notes; 3. clarification |
| | | |
| Section to be changed | | Section 4.1.4.1 |
| Description of change | | “if needed” added to the following sentence:). At Visits 2 - 4 detailed instructions on the use of the devices will be repeated if needed, but patients should not inhale from a training device that day. |
| Rationale for change | | Clarification |
| | | |
| Section to be changed | | Table 4.2.2.1:1 |
| Description of change | | 1. Footnote 2 - corrected q.i.d to qd; 2. LAMA/LABA combination during screening, NOT permitted (w/o 4 wks. prior to V2) changed to 3 weeks prior to V2 |
| Rationale for change | | errors |
| | | |
| Section to be changed | | Section 7.3 |
| Description of change | | Added: This set will be called Full Analysis Set (FAS). |
| Rationale for change | | Inadvertently left out of protocol |
| | | |
| Section to be changed | | RDC updated to EDC in several places |
| Description of change | | RDC (Remote Data Capture) is the brand name of Oracle’s EDC (electronic Data Capture System) |
| Rationale for change | | Correctness |
| | | |
| Section to be changed | | Section 4.3 |
| Description of change | | Medication compliance updated from 80-100% to 80-120% |
| Rationale for change | | Correction |
| | | |
| Section to be changed | | Section 4.1.4 |
| Description of change | | The Diskus Inhaler should not be used beyond one month after removal from the moisture-protective foil overwrap, or after all blisters have been used (when indicator reads “0”), whichever comes first. |

| | | |
|------------------------------|--|---|
| Rationale for change | | Clarification on timeframe to use Diskus device once opened |
| | | |
| Section to be changed | | Section 4.1.6 |
| Description of change | | The Diskus Inhaler should not be used beyond one month after removal from the moisture-protective foil overwrap, or after all blisters have been used (when indicator reads “0”), whichever comes first. |
| Rationale for change | | Clarification on timeframe to use Diskus training device once opened |
| | | |
| Section to be changed | | Section 6.2.1 |
| Description of change | | Patients will be assigned a study patient number in the EDC system once consent is signed. This is populated from the IRT system; therefore, the site should also register the patients as screened in IRT. |
| Rationale for change | | Corrected based in implementation of new systems |

APPROVAL / SIGNATURE PAGE**Document Number: c13020187****Technical Version Number:3.0****Document Name: clinical-trial-protocol-version-03**

2. LIST OF ABBREVIATIONS

Include a list of all abbreviations used in the TSAP

Term	Definition / description
ADS	Analysis Data Set
AE	Adverse event
ANCOVA	Analysis of Covariance
ATC	Anatomical Therapeutic Classification
AUC	Area Under the Curve
BDI	Baseline Dyspnoea Index (Mahler)
BRPM	Blinded report planning meeting
CD	Concomitant diagnosis
CML	Clinical Monitor Local
COPD	Chronic Obstructive Pulmonary Disease
CRA	Clinical Research Associate
CT	Concomitant treatment
CTP	Clinical Trial Protocol
CTR	Clinical Trial Report
DBL	Data Base Lock
DH	Digital Health
DM&SM	Boehringer Ingelheim Data Management and Statistics Manual
DRA	Drug Regulatory Affairs
eCRF	electronic Case Report Form
EoT	End of Text
EMA	European Agency for the Evaluation of Medicinal Products
FAS	Full analysis set

Term	Definition / description
FDC	Fixed Dose Combination
FEV ₁	Forced Expiratory Volume in One Second
FVC	Forced Vital Capacity
ICF	Informed Consent Form
ICH	International Conference on Harmonisation
(I)PV	(Important) Protocol Violation
IVRS	Interactive Voice Response System
LOCF	Last observation carried forward
MedDRA	Medical Dictionary for Regulatory Activities
MMRM	Mixed effects model repeated measures
MQRM	Medical Quality Review Meeting
PEF	Peak Expiratory Flow
PFT	Pulmonary Function Test
PK	Pharmacokinetics
PPS	Per protocol set
PRN	Pro re nata (when necessary)
PSTAT	Project Statistician
PT	Preferred term
Q1	Lower quartile
Q3	Upper quartile
REML	Restricted maximum likelihood
RS	Randomised set
SABA	Short-acting beta agonist
SAE	Serious Adverse Event
SAMA	Short-acting muscarinic antagonist
SD	Standard deviation
SGRQ	Saint George's Respiratory Questionnaire
SMQ	Standardised MedDRA query
SOC	System organ class
TDI	Transitional Dyspnoea Index
TS	Treated set

Proprietary confidential information © 2019 Boehringer Ingelheim International GmbH or one or more of its affiliated companies

Term	Definition / description
TSAP	Trial statistical analysis plan
TTM	Termination of trial medication

3. INTRODUCTION

As per International Conference on Harmonisation (ICH) E9 (1), the purpose of this document is to provide a more technical and detailed elaboration of the principal features of the analysis described in the protocol, and to include detailed procedures for executing the statistical analysis of the primary and secondary variables and other data.

This Trial Statistical Analysis Plan (TSAP) assumes familiarity with the Clinical Trial Protocol (CTP), including Protocol Amendments. In particular, the TSAP is based on the planned analysis specification as written in CTP Section 7 “Statistical Methods and Determination of Sample Size.” Therefore, TSAP readers may consult the CTP for more background information on the study, e.g., on study objectives, study design and population, treatments, definition of measurements and variables, planning of sample size, randomisation.

SAS® Version 9.4 or later will be used for all analyses.

4. CHANGES IN THE PLANNED ANALYSIS OF THE STUDY

In addition to the further endpoints described in the protocol, the following further endpoints will be added.

- FEV1 AUC 0-12 h response (change from baseline) [L] after 6 weeks treatment
- FVC AUC0-24h response (change from baseline) [L] after 6-weeks treatment
- FVC AUC0-12h response (change from baseline) [L] after 6-weeks treatment
- FVC AUC 12-24h response (change from baseline) [L] after 6-weeks of treatment

5. ENDPOINTS

5.1 PRIMARY ENDPOINTS

Primary endpoint of efficacy will be used as described in the clinical trial protocol, section 5.1.1.

5.2 SECONDARY ENDPOINTS

5.2.1 Key secondary endpoints

There are no key secondary endpoints in this trial.

5.2.1 (Other) Secondary endpoints

Secondary endpoints of efficacy will be used as described in the clinical trial protocol, Section 5.1.2.

6. GENERAL ANALYSIS DEFINITIONS

6.1 TREATMENTS

As described in Section 4 of the CTP, the following treatments are planned to be investigated in this study:

Table 6.1: 1 Treatment and labels

Treatment	Label
Tiotropium + olodaterol FDC (5 µg / 5 µg) inhalation solution	T+O 5/5
Fluticasone propionate + salmeterol FDC (250 µg / 50 µg) inhalation powder	F+S 250/50

This is a parallel-group trial consisting of a screening and run-in period of at least 4 four week duration, a 12-week randomised treatment period and a three week (21 days) follow up period

For the main safety analysis, data occurring during the treatment period between first double-blind drug intake date and within 21 days after the last drug intake date is assigned to and analysed under the respective treatment. Data occurring before the first drug intake date is assigned to screening/run-in period. Data more than 21 days after the end of the last treatment period and up to and including the date of the study termination will be assigned to follow-up.

Any cases of patient being treated with the wrong study medication will be identified and summarized as an important protocol violation.

- If a patient was treated with a study medication different from the randomized treatment throughout the on-treatment period, this patient will be included in the treated set and will be analysed as treated under the initial study medication received on Day 1 for both efficacy and safety analyses. Such a case will be reported as an important protocol violation and this patient will be excluded from the per-protocol set (PPS)
- If a patient was treated with incorrect study medication during part of the on-treatment period, this patient will be included in the treated set and will be analysed under the initial study medication received on Day 1 for both efficacy and safety analyses. For safety analyses, the actual incorrect study medication is listed as the actual treatment at onset of any adverse event in the subject data listings. Such a case will be reported as an important protocol violation and a decision will be made whether to exclude this patient from the PPS at the blinded report planning meeting (BRPM) on a case-by case basis before unblinding.

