4.1.4 Drug assignment and administration of doses for each patient

Dispensing of trial medication

Patients will be randomized at Visit 2 to one of two treatments, tiotropium+olodaterol FDC and placebo fluticasone propionate+salmeterol FDC or fluticasone propionate+salmeterol FDC and placebo tiotropium+olodaterol FDC. At Visit 2 the IRT will assign three Respimat[®] Kits (two for treatment and one for reserve) and three Diskus[®] Kits (two for treatment and one for reserve). At Visit 3 the patient will bring in all treatment kits (including the reserve kits) that were dispensed at Visit 2. At Visit 3, two new Respimat[®] and Diskus[®] treatment kits will be dispensed in addition to the reserve kit which was previously dispensed at Visit 2. If the reserve kit dispensed at Visit 2 was used by the patient, a new reserve kit will be dispensed as well. Each treatment kit will have a unique medication ID number. Trial medication will be dispensed to the patient by the investigator/pharmacist at these visits. The amount of trial medication dispensed will be recorded on the drug accountability forms.

The reserve kits allow the patient the flexibility of not having to return to the clinic immediately to replace a lost or malfunctioning inhaler. In the event that a patient may need additional inhalers and cartridges due to rescheduled visits, inhaler loss or malfunction, these will be supplied on an 'on demand' basis. Dispensing of these extra inhalers will also be managed via the IRT.

Priming of the Respimat[®] Inhaler

Each newly assembled Respimat[®] Inhaler has to be primed. Priming should NOT take place in the same room where the patient is inhaling trial medication. The inhaler should be primed by actuating it until an aerosol is visible plus three additional actuations. All priming actuations should be directed to the ground. For detailed priming instructions please refer to the Respimat[®] Inhaler handling instructions in [Appendix 10.1](#).

Once assembled, the shelf-life of the Respimat[®] Inhaler with trial medication is 3 months. Once assembled, the shelf-life of the Respimat[®] Inhaler with training medication is also 3 months. Therefore it is important to ALWAYS enter the date of the cartridge insertion on the medication label of the Respimat[®] Inhaler immediately after the cartridge is inserted.

Fluticasone propionate+salmeterol Inhaler - Diskus[®]

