7.3 PLANNED ANALYSES

The efficacy analysis will be performed in all randomized patients who were documented to have received any dose of trial medication and who have both baseline and any evaluable post-baseline measurement for at least one of the efficacy endpoints. This set will be called Full Analysis Set (FAS).

After blinded review of the magnitude and potential impact of any important protocol violations, a subset of the data corresponding to those patients without any important deviations from the protocol will be created. This will be called the Per-Protocol Set (PPS). If the number of patients in PPS is less than 90% of the number of patients in FAS, the

primary analyses for the primary efficacy endpoint will also be performed on PPS. These will be supportive analyses.

All randomised patients taking any dose of the trial medication will be included in the safety evaluation (Treated Set).

The handling of randomised patients who received the wrong treatment will be specified in the TSAP”

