7.7 DETERMINATION OF SAMPLE SIZE

Calculations were performed using nQuery Advisor[®] 6.1 statistical package by Statistical Solutions Ltd.

Assuming a standard deviation of 0.22L a total sample size of 274 completed patients, will be able to detect a treatment difference of .075 L, for FEV₁ AUC_{0-24h} with 80% power, using a two-sided test at $\alpha=0.05$ for superiority testing. The assumptions for sample size calculation are based on the results of 1237.5, 1237.6, and 1237.11 studies. Assuming a maximum 5% drop-out rate, in order to ensure that 274 completers, 288 patients will be randomized.

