	A1	Inclusion Criteria not met	Any of inclusion criteria 2 through 6 not met as specified in the protocol.	PPS
	A2	Exclusion Criteria not met	Any of exclusion criteria 2, 3, 9, 12,13, 15, 16, 17, 19, 20, 24, 25 not met as specified in the protocol Any of exclusion criteria 1,4, 5, 6, 7, 8, 10, 11, 12, 14, 18, 21, 22, 23 not met as specified in the protocol	PPS None
B		Informed Consent		
	B1	Informed consent not available /not done	Informed consent date missing; no signature on ICF	All
	B2	Informed consent too late	Date of informed consent was after the date of any study related procedure. If the date of informed consent equals to date of Visit 1, such cases are discussed at MQRM/ BRPM/DBL meetings. Patient signed the wrong version of ICF and then signed correct version with date after randomisation	None
C		Trial medication and randomisation		
	C1	Incorrect trial medication taken	Not throughout study; could be at a clinic visit or between clinic visits	PPS (decision at BRPM)
	C2	Randomisation order not followed and incorrect trial medication taken	Throughout the study, check IVRS	PPS
	C3	Non-compliance with study medication		
	C3.2	Serious non-compliance with study medication as reported in monitoring report	Decision at MQRM/BRPM If at visit 4	PPS
	C4	Medication code broken inappropriately	To be discussed and decided during MQRM/BRPM. Only inappropriate code breaks are IPVs (e.g. unblinding by Global Pharmacovigilance is not).	PPS

Table 6.2: 1 (cont.) Important protocol violations

Category Code	Description	Requirement	Excluded from
D	Concomitant medication		
D1	Improper medication washout at baseline visit or at primary endpoint visits	Visit 2 and Visit 4, refer to Section 4.2.2.2 and Table 4.2.2.1:1 in CTP. Decision at BRPM	PPS
D2	Prohibited medication use during the study	Refer to Table in 4.2.2.1:1 in CTP. Decision at BRPM if in week prior to Visit 2 or Visit 4.	PPS
F	Incorrect timing		
F3	Primary endpoint recorded outside time window		
F.3.1	PFT measurement at 12-hour time point performed more than 13 hours after dosing	Visit 4 Decision at BRPM	PPS
F3.2	PFT measurement at 23:00 or 24:00 planned time performed earlier than 22 hours after dosing at primary endpoint visit(s)	Visit 4 Decision at BRPM	PPS
F4	Trial medication		
F4.1	Trial medication taken prior to pre-dose measurement at baseline visit	Visit 2 Decision at BRPM	PPS
F4.2	Trial medication taken prior to pre-dose measurement at primary endpoint visit(s)	Visit 4 Decision at BRPM	PPS

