6.3 PATIENT SETS ANALYZED

There are four patient sets defined in this trial:

- **Randomised Set (RS)**
 This patient set includes all patients who signed the informed consent form and were also randomised, regardless whether the patient was treated with trial medication or not.
- **Treated Set (TS)**
 All randomized patients who were dispensed trial medication and were documented to have taken any dose of trial medication.
- **Full Analysis Set (FAS)**
 This patient set is nested within the TS and includes patients who had baseline and at least one post-baseline measurement for at least one efficacy endpoint. The FAS will be used for the primary analyses of the primary efficacy endpoint and for all other efficacy endpoints.
- **Per Protocol Set (PPS)**
 This patient set is nested within the FAS and only includes patients who had no important PVs which are specified to be excluded from the efficacy analysis. (see [Table 6.2: 1](#)).
- The final decision regarding which patients are included in PPS will be made at BRPM prior to data unblinding.

If the number of patients in PPS is less than 90% of the number of patients in FAS, the primary analysis for the primary endpoint will also be performed on the PPS as supportive analyses.

The analysis will be compliant with ICH guideline [\(5\)](#)

Table 6.3: 1 Patient sets analyzed

Class of endpoint	Treated set	Patient set	
		FAS	PPS
Primary endpoint		primary analysis	*supportive analysis
Key secondary, (other) secondary and further endpoints		X	
Safety	X		
Demographic/baseline	X		

* If the number of patients in PPS is less than 90% of the number of patients in FAS, the primary analysis for the primary endpoint will also be performed on the PPS as supportive analyses.

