7.8.1 Adverse events

Unless otherwise specified, the analyses of adverse events will be descriptive in nature. All analyses of AEs will be based on the number of subjects with AEs and NOT on the number of AEs.

For analysis multiple AE occurrence data on the CRF will be collapsed into an AE provided that all of the following applies:

- All AE attributes are identical (LLT, intensity, action taken, therapy required, seriousness, reason for seriousness, relationship, outcome).
- The occurrences were time-overlapping or time-adjacent (time-adjacency of 2 occurrences is given if the second occurrence started on the same day or on the day after the end of the first occurrence).

For further details on summarization of AE data, please refer to [\(3, 4\)](#).

The analysis of adverse events will be based on the concept of treatment emergent adverse events. That means that all adverse events occurring between first drug intake till last drug intake + residual effect period will be assigned to the randomised treatment. All adverse events occurring before first drug intake will be assigned to 'screening' and all adverse events occurring after the residual effect period will be assigned to 'post-treatment' (for listings only). For details on the treatment definition, see [Section 6.1](#).

According to ICH E3 AEs classified as 'other significant' needs to be reported and will include those non-serious and non-significant adverse events with
(i) 'action taken = discontinuation' or 'action taken = reduced', or
(ii) marked haematological and other lab abnormalities or lead to significant concomitant therapy as identified by the Clinical Monitor/Investigator at a Medical Quality Review Meeting.

An overall summary of adverse events will be presented.

The frequency of subjects with adverse events will be summarised by treatment, primary system organ class and preferred term (mention MedDRA levels to be displayed in the tables). Separate tables will be provided for subjects with other significant adverse events according to ICH E3 and for subjects with serious adverse events.

The system organ classes will be sorted alphabetically, preferred terms will be sorted by frequency (within system organ class).

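### SAP 6.1 places a patient wrongly dosed on Day 1 in the arm of the drug taken for the primary efficacy analysis, and no efficacy analysis by randomised arm is planned for such patients

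*SAP*

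**What the plan says.** Protocol 7.3 sets no rule of its own: "The handling of randomised patients who received the wrong treatment will be specified in the TSAP". SAP 6.1 supplies it in two bullets.

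- **Wrong drug throughout the treatment period.** The patient "will be analysed as treated under the initial study medication received on Day 1 for both efficacy and safety analyses", and is excluded from the per-protocol set (PPS).
- **Wrong drug for part of the period.** The patient "will be analysed under the initial study medication received on Day 1 for both efficacy and safety analyses". PPS exclusion is decided case by case at the blinded report planning meeting.

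SAP Table 6.2: 1 lists these errors as C1 (wrong medication for part of the study) and C2 ("Randomisation order not followed and incorrect trial medication taken"). Both lead to exclusion from the PPS only. SAP 6.3 says: "The FAS will be used for the primary analyses of the primary efficacy endpoint and for all other efficacy endpoints". The affected patients therefore stay in the primary analysis.

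Protocol 4.1.4 has Respimat and Diskus kits assigned separately: "Each treatment kit will have a unique medication ID number".

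**The concern.** A patient whose Day 1 drug differed from the randomised one is counted in the opposite arm in the primary MMRM. A patient who starts correctly and later receives a wrong kit is not moved. Arm membership in the only confirmatory test then depends on an event after randomisation. The comparison is protected from confounding only if dosing errors are unrelated to prognosis. Analysis by randomised arm does not need that assumption.

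The rule is also incomplete for a double-dummy design. If one device is wrong on Day 1, the patient receives two actives or two placebos. The drug received on Day 1 then identifies neither of the two treatment labels in SAP Table 6.1: 1, so the patient has no defined arm in the primary analysis.

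**Working it through.** **Does any other planned analysis use the randomised arm for these patients?**

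| Place | Content | Supplies efficacy by randomised arm? |
|---|---|---|
| SAP 6.3, FAS | Nested in the treated set; not described as analysed by randomised treatment | No |
| SAP 6.3, Randomised Set | Defined, but given no analysis in Table 6.3: 1 | No |
| SAP 6.3 and 7.4, PPS repeat | Run only if the PPS is below 90% of the FAS; drops C2 patients, and C1 patients by decision | No |
| SAP 7.4, model code | The treatment variable is called only treatment, without saying planned or actual | Does not override 6.1 |
| SAP 7.4.1 | Sensitivity analysis for missing data | No |
| SAP 7.5.2 | Secondary endpoints, same model | No |

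The Day 1 rule can also pick an arm that is neither the one randomised nor the one being taken at Week 12. Each kit lasts about 30 days and new kits are dispensed at Visit 3. A patient whose first two devices were both wrong and whose later kits were all correct is on the randomised drug at Week 12, yet SAP 6.1 counts that patient in the opposite arm.

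**Reproducing the plan's sample size.** Protocol 7.7 gives a difference of 0.075 L, two-sided alpha of 0.05 and 80% power: "Assuming a standard deviation of 0.22L a total sample size of 274 completed patients". A two-sample t-test has 79.99% power with 136 per arm and 80.28% with 137 per arm. So 2 × 137 = 274 is reproduced.

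**Size of the effect.** The documents give no rate of dosing errors. Assume k patients per arm of 144 (288/2) take the other arm's drug throughout, unrelated to prognosis, with a true difference of 0.075 L.

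- Standard error: 0.22 × √(2/137) = 0.0266 L.
- Each arm's as-randomised mean moves towards the other by (k/144) × 0.075 L, so the difference shrinks by (2k/144) × 0.075 L.
- Power: two-sided 5% t-test, 137 per arm, at the reduced difference.

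| k per arm | Reduction (L) | Reduction / SE | As-randomised difference (L) | Power |
|---|---|---|---|---|
| 0 | 0 | 0 | 0.0750 | 80.3% |
| 1 | 0.0010 | 0.04 | 0.0740 | 79.2% |
| 3 | 0.0031 | 0.12 | 0.0719 | 76.9% |
| 5 | 0.0052 | 0.20 | 0.0698 | 74.4% |

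k = 5 means 10 of 288 patients (3.5%) fully swapped, which is an upper scenario. With 137 instead of 144 as the denominator of the dilution, power is 79.1%, 76.7% and 74.1%.

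A simulation of 20,000 trials with 144 per arm agrees. The as-treated estimate averages about 0.075 L for k = 1 and k = 5. The as-randomised estimate averages about 0.074 L and 0.070 L. Both average about zero under the null.

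The t-test stands in for the MMRM, which also adjusts for baseline and uses the Week 6 data, so the power figures are approximate.

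**The case against.** **The rule is prespecified and mechanical.** It leaves no choice of arm after results are known. The protocol delegates the matter to the SAP, so no protocol rule is breached. All wrong-drug cases must be identified and summarised as important protocol violations, and PPS decisions are made before unblinding. All of this is correct. It makes affected patients visible, but it does not restore the randomised comparison.

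**Cases should be rare.** Assignment is blinded and by IRT. If no Day 1 error occurs, the FAS analysis is already the analysis by randomised arm. This stands and limits the weight of the point.

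**The figures measure the cost of the fix, not the harm of the rule.** Under the stated assumptions the Day 1 rule keeps the estimate at 0.075 L and power at 80.3%, with no expected bias under the null. This also stands. The reductions in the table are dilution, not confounding bias. The harm would arise if errors were related to prognosis, and the documents give nothing from which to size that. The case for change rests on not needing the assumption and on every patient having a defined arm.

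**The one-device error is hypothetical.** Nothing suggests it is expected. It is possible because the kits are separate, but it is secondary to the main point.

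**Conclusion.** The concern holds. SAP 6.1 assigns the efficacy arm by Day 1 drug, the affected patients remain in the FAS, and no planned efficacy analysis places a patient wrongly dosed on Day 1 in the randomised arm. The numerical effect is likely to be small or nil: 0.04 to 0.20 standard errors between the two analyses for 1 to 5 assumed full swaps per arm, and zero under the null if errors are unrelated to prognosis. The change should be made because it is cheap and keeps the only confirmatory test a comparison of randomised groups. It does not invalidate the design or alter the sample size.

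**What to change.** 1. In both bullets of SAP 6.1, state that FAS efficacy analyses use the randomised treatment and that safety analyses on the treated set use the Day 1 treatment.
2. Keep the PPS exclusions as they are. Efficacy by Day 1 treatment may be kept as a sensitivity analysis.
3. State how a patient with one wrong device on Day 1 (two actives or two placebos) is labelled for safety, and for the Day 1 efficacy sensitivity analysis if it is kept.
4. Reconcile SAP 7.8.1 with 6.1. Section 7.8.1 assigns adverse events by randomised treatment and then refers the reader to 6.1 ("For details on the treatment definition"), which uses the Day 1 drug for safety. Wording 7.8.1 as treatment as defined for safety in Section 6.1 removes the conflict.

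The cost is a few SAP sentences before unblinding, with no operational change. If full swaps occur and the true difference is 0.075 L, the analysis by randomised arm loses about 1 to 6 points of power for k = 1 to 5 (80.3% falling to 79.2% or 74.4%).
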